## 2 STUDY OBJECTIVES

The primary objectives of the study are to:

- Evaluate the safety and tolerability of 12 weeks of treatment with either a 200 mg po BID dose of EBP-994, or a 300 mg po BID dose of EBP-994, in subjects chronically infected with HDV genotype 1
- Evaluate the pharmacodynamic (PD) activity of a 200 mg po BID dose of EBP-994, vs. a 300 mg po BID dose of EBP-994 on HDV viral load
- Evaluate the pharmacokinetic (PK) profile of a 200 mg po BID dose of EBP-994 vs. a 300 mg po BID dose of EBP-994 in subjects chronically infected with HDV genotype 1
- Evaluate the safety, tolerability, PK, and HDV viral load of a treatment up to 48 weeks with EBP-994 alone, or in combination with Norvir® and/or Pegasys® in subjects chronically infected with HDV

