### Study Objectives

The primary objectives of the study are to:

- Evaluate the safety and tolerability of 12 weeks of treatment with a 200 vs. 300 mg PO BID dose of EBP-994 in subjects chronically infected with HDV
- Evaluate the pharmacodynamic (PD) activity of a 200 vs. 300 mg PO BID dose of EBP-994 on HDV viral load
- Evaluate the pharmacokinetic (PK) activity of a 200 vs. 300 mg PO BID dose of EBP-994
- Evaluate the safety, tolerability, PK, and HDV viral load of a treatment up to 48 weeks with EBP-994 alone and in combination with Norvir® and/or Pegasys® in subjects chronically infected with HDV

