### Study Design

This study is a phase II, randomized, open-label study up to 48 weeks of treatment with EBP-994 alone, or in combination with Norvir® and/or Pegasys® in subjects chronically infected with HDV genotype 1. The duration of the study for each subject will last approximately 11-55 weeks (up to three week screening period, 4-48 week treatment period and four week safety follow-up period. The duration of the entire study is anticipated to be approximately 45 months (first subject in to last subject out). The investigator is free to initiate licensed medications at any time point and decrease the dose of EBP-994 if deemed warranted for GI side effects.

This study will explore EBP-994 in four groups of treatments:

Group 1: EBP-994 (up to 600 mg daily dose) monotherapy

Group 2: EBP-994 (up to 200 mg daily dose) in combination with Norvir®

Group 3: EBP-994 (up to 600 mg daily dose) in combination with Pegasys®

Group 4: EBP-994 (up to 150 mg daily dose) in combination with Norvir® and Pegasys®

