### **Clinical Safety Summary**

There are currently no HDV-specific therapies. EBP-994 could be the first direct acting anti-HDV agent by disrupting the HDV life cycle through inhibition of prenylation at the level of host cell farnesyl-transferase. EBP-994 has been dosed in human studies examining PK and PD and has exhibited inhibition of farnesyl transferase at levels below the maximally tolerated dose (MTD; 300 mg BID). A risk associated with the use of direct acting antiviral agents would be the development of resistance by the virus. However, because prenylation is a host function not coded for by the HDV genome, the risk of resistance development could be mitigated. Viral surveillance will be conducted throughout the conduct of the study to assess the risk of viral resistance. Two doses of EBP-994 alone, or in combination with Norvir® and/or Pegasys® will be examined in this proof-of-concept study, 200 vs. 300 mg

(PO BID), and the adverse profile will be correlated to the clinical benefit of viral suppression.

Other risks that may be encountered with the treatment of HDV include an increase in liver function tests during and after therapy, the risk of a flare in HBV ( $\geq 1$  log increase in HBV viral load) as the HDV viral load goes down, and an increase in HDV viral load after therapy is ended. Flares in liver function tests are not uncommon with the start of treatment of HBV disease and necessitate a careful and frequent review of liver function studies. We will follow the same approach in this study unless there is a concomitant flare in HBV viral load. A flare of HBV viral load while on EBP-994 will be treated by starting specific anti-HBV therapy using one of the 5 approved drugs, the selection being made by the Investigator based on the subject's condition and history of prior anti-HBV therapy. A flare in HDV viral load after the termination of EBP-994 will be watched closely and interferon therapy may be started as determined by the investigator.

Finally, the known adverse event profile for EBP-994 (and all other prenylation inhibitors in clinic) is primarily gastrointestinal, primarily dose related diarrhea as well as nausea and vomiting.

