## **6.2 Study Visit 2 (Day 1) - Treatment Period**

This Study Visit marks the beginning of the twenty-four weeks treatment Period in which subjects will receive EBP-994 treatments (EBP-994 alone or in combination with Norvir® and/or Pegasys®). Subjects will be admitted to the unit on the morning of Day 1 in a fasted

state (nothing to eat or drink except water) and will receive a standard breakfast between 45 - 30 minutes prior to scheduled dosing time.

The following evaluations and procedures will be performed at Study Visit 1 (see Appendix A for summary):

1. Brief physical examination pre-dose (performed by a physician, nurse practitioner, physician's assistant or nurse). This includes weight and vital signs as well as HEENT, heart, lungs, abdomen and lower extremity.
2. Vital signs pre-dose and after the post-dose ECG (BP after being seated for 5 minutes, pulse, respiratory rate and temperature)
3. Concomitant medications will be recorded
4. Adverse events will be recorded
5. 12-Lead ECG
6. Randomization

Subjects will be randomized to one of the following groups:

Group 1: EBP-994 (up to 600 mg daily dose) monotherapy  
Group 2: EBP-994 (up to 200 mg daily dose) in combination with Norvir®  
Group 3: EBP-994 (up to 200 mg daily dose) in combination with Pegasys®  
Group 4: EBP-994 (up to 200 mg daily dose) in combination with Norvir® and Pegasys®

7. Laboratory studies (Pre-Dose) (non-fasting):
  - a. Serum chemistry panel, including liver function tests and albumin
  - b. Complete blood count (CBC with differential and platelet count)
  - c. Quantitative PCR for HDV viral load
  - d. Blood samples (plasma and serum) for viral mutation analysis, resistance phenotyping, and analysis of drug mechanism and treatment response. These analyses include molecular and genetic analysis of drug mechanism, viral/host factors influencing treatment response (e.g. genotype and subgenotype analysis, quasispecies analysis, determination of drug and potential metabolite levels in plasma).
  - e. Urinalysis
  - f. Urine pregnancy test (child-bearing females only)

- g. Blood sample for monitoring immunologic changes in peripheral blood mononuclear cells (PBMC).
- 8. Pharmacokinetic blood samples (at the following time points: 0-pre-dose, post dose: 15 min, 30 min, 60 min, 90 min, 2h, 2.5 h, 3 h, 4 h, ,6 h, 8, 10, 12 h) (for those subjects participating in the PK portion of this trial)
- 9. Dosing Instructions:  

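### The primary objectives contrast 200 with 300 mg BID, but no assignment to either dose is described, the dose ceilings for Groups 3 and 4 conflict, and Section 8 groups no analysis by dose

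*Combined protocol and SAP*

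**What the plan says.** The PD objective in Section 2 is to "Evaluate the pharmacodynamic (PD) activity of a 200 mg po BID dose of EBP-994, vs. a 300 mg po BID dose", measured on HDV viral load. The PK objective sets the same two doses against each other. For safety, Section 2 names the two doses as alternatives, but the synopsis makes them a contrast: "Evaluate the safety and tolerability of 12 weeks of treatment with a 200 vs. 300 mg PO BID dose of EBP-994". The Clinical Safety Summary in Section 1.2 goes further: "Two doses of EBP-994 alone, or in combination with Norvir® and/or Pegasys® will be examined in this proof-of-concept study, 200 vs. 300 mg".

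Randomisation is described in Section 6.2, item 6, and Section 3 says that the group decides which co-medication is given. The groups are EBP-994 alone, with Norvir, with Pegasys, or with both. Group 1 reads "Group 1: EBP-994 (up to 600 mg daily dose) monotherapy" in Section 6.2, and the synopsis gives the same limit. Groups 3 and 4 differ between the two places:

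- Synopsis: "Group 3: EBP-994 (up to 600 mg daily dose) in combination with Pegasys"; Section 6.2: "Group 3: EBP-994 (up to 200 mg daily dose) in combination with Pegasys".
- Synopsis: "Group 4: EBP-994 (up to 150 mg daily dose) in combination with Norvir® and Pegasys"; Section 6.2: "Group 4: EBP-994 (up to 200 mg daily dose) in combination with Norvir® and Pegasys".

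Investigators may lower the EBP-994 dose for GI effects and may start licensed therapy, including Pegasys, at any time (Section 3; synopsis, Safety).

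**The concern.** A comparison of two doses needs a rule for who receives each dose and a rule for who is counted under each. The documents give neither.

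The second gap matters because doses can change. If results are summarised by the four groups, 200 and 300 mg BID are pooled, and only the by-subject listings and graphs bear on the PD objective. If they are summarised by dose received, subjects reduced from 300 mg because of GI effects count as 200 mg subjects. Section 1.2 itself calls the diarrhoea dose related, so that contrast would be mixed with tolerability. In an open-label study, an unstated choice between the two could be made after the data are seen.

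The ceiling conflict is a separate and more concrete problem. It leaves the maximum dose in two of the four groups undefined. That bears on safety, and on the fourth objective, which evaluates EBP-994 alone and in these combinations.

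**Working it through.** Section 8.7 gives no sample-size calculation, so there is no figure to reproduce. The check compares dose requirements with ceilings, then reads Section 8 for a dose grouping.

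**1. Daily dose required.** 2 × 200 = 400 mg/day; 2 × 300 = 600 mg/day.

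**2. Ceilings (mg/day).**

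| Group | Synopsis | Section 6.2 | Can it hold 400 or 600 mg/day? |
|---|---|---|---|
| 1, alone | 600 | 600 | Both doses, in both places |
| 2, Norvir | 200 | 200 | Neither |
| 3, Pegasys | 600 | 200 | Both under the synopsis; neither under 6.2 |
| 4, Norvir and Pegasys | 150 | 200 | Neither |

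Against a ceiling of 200 mg/day, the two regimens are 400/200 = 2.0 and 600/200 = 3.0 times too high. Against 150 mg/day they are 400/150 = 2.7 and 600/150 = 4.0 times too high. So one group of four (6.2) or two of four (synopsis) can hold the contrast. Neither Norvir group can, although Section 1.2 includes them.

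**3. Size of the conflict.** Group 3: 600/200 = 3. Group 4: 200/150 = 1.33, so a site following 6.2 could dose a third above the synopsis limit.

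**4. A ceiling does not identify a regimen.** Section 5.2 allows dosing every 8, 12 or 24 hours. A total of 600 mg/day could be 2 × 300 or 3 × 200.

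**5. Section 8.**
- 8.4.1: the one stated by-group summary is of adverse events leading to withdrawal. It is by treatment group, not dose.
- 8.5: dose appears only as the amount administered in the clearance and volume formulas.
- 8.5.1: Day is the only fixed effect named in the ANOVA.
- 8.6: viral load means and medians are by timepoint; listings are by subject.

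**6. Effect of a dose reduction on 8.5.1.** This section compares Day 28 AUC with Day 1 AUC. Assume that AUC is proportional to dose, which the documents do not establish. A subject reduced from 300 to 200 mg before Day 28 then has the ratio multiplied by 200/300 = 0.67. If a fraction r of 300 mg starters is reduced, their geometric mean ratio is multiplied by (2/3)^r: 0.92 at r = 0.2 and 0.85 at r = 0.4. These values of r are assumed, since no reduction rate is given. The direction is what matters: reductions would look like lower accumulation.

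**7. Where dose in mg can be found.** The diary (6.2, Dosing Instructions) records date, time and number of capsules. Capsules come as 25, 50 or 75 mg (5.1). Four of 50 mg make 200 mg; four of 75 mg make 300 mg. A count alone need not separate the two doses.

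**The case against.** The best defence is that this is an open-label pilot with a descriptive viral-load plan and no claim to statistical sizing. Its objectives are to evaluate, not to test. By-subject listings and graphs are planned, so a by-dose description remains possible if doses are recorded. The Section 1.2 sentence is background narrative, and under the synopsis one combination group can indeed hold both doses. In Section 2 the safety objective is not worded as a comparison.

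Much of that stands. It means that no test is invalidated and that nothing follows about power. It does not supply the missing dose label or reconcile two current statements of the same ceiling.

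A reader might infer that the dose contrast is definitely non-randomised. The documents do not support that; they are silent on how dose is assigned. The synopsis dosing plan and Section 3 say that treatment duration depends on the assigned group, yet the four listed groups carry no durations. The assigned group may therefore be finer than the four labels, and dose could be part of it. What can be said is that no randomised or other dose assignment is described.

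A reader might also want a figure for the precision of the dose difference, or for the bias from reclassified subjects. Either would need assumed enrolment (75 is a cap), allocation, dose split, variability and reduction rates. The documents give none of these, so no such figure forms part of this point.

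**Conclusion.** The point holds in this form. Two primary objectives, and a third in the synopsis wording, contrast doses for which the documents describe no assignment and no analysis grouping. At most two of the four groups can hold those doses, and only one under Section 6.2. The Group 3 ceiling differs threefold between two current sections, and the Group 4 ceiling by a third. These statements rest on the text and simple arithmetic alone. The multiplier of 0.67 in the AUC comparison also assumes dose-proportional exposure, and the values 0.92 and 0.85 further assume reduction rates.

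This should be fixed, but it does not undermine the study. It limits what the stated objectives can show and leaves a dosing limit ambiguous. It does not show that the dose comparison is biased.

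**What to change.** 1. Give Groups 3 and 4 the same ceilings in the synopsis and Section 6.2. Limit the Section 1.2 sentence to the group or groups that can hold 200 or 300 mg BID. Which ceilings are correct is for the sponsor to say.
2. State in Section 6.2 how the starting dose is assigned. If it is not randomised, word the safety objective in the synopsis and the PD and PK objectives as descriptive, non-randomised evaluations of the two doses.
3. In Section 8, summarise safety and viral load by starting dose within treatment group, regardless of later reduction. Flag subjects who start Pegasys or other licensed therapy outside their assigned group.
4. Report PK by the dose taken at sampling, and dose-normalise AUC in the Section 8.5.1 comparison of Day 28 with Day 1. Take dose in mg from the dispensing and accountability records (5.5), the CRF entries on dose changes (7.1.1, item 6) and the dose given at the Day 28 visit (6.7), not from the capsule-count diary alone.

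The cost is wording, two reconciled limits and the added analysis rules; no patients, visits or samples are added. Summarising by starting dose dilutes the difference between the doses, so the dose claim becomes weaker. Dose-normalising removes the effect of reductions fully only if exposure is proportional to dose.

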## 3 STUDY DESIGN

This study is a phase II, randomized, open label study of up to 48 weeks of treatment with EBP-994 alone, or in combination with Norvir® and/or Pegasys® in subjects chronically infected with HDV genotype 1. The investigator is free to initiate licensed medications at any time point and decrease the dose of EBP-994 if deemed warranted for GI side effects. The duration of the study for each subject will be approximately 11-55 weeks (up to three week screening period, up to 48 week treatment period and four week safety follow-up period).

The duration of the entire study is anticipated to be approximately 36 months (first subject in to last subject out). Pharmacokinetic sampling will be done at Day 1 and Day 28 of dosing. PK sampling will be conducted only on subjects who have consented to participate in the PK portion of this study. Participation in PK sampling is optional for each subject.

At the Screening Visit, subjects giving written informed consent will have all required evaluations to determine their eligibility to participate in the study. The outpatient screening visit must occur within 21 days of Study Visit 1.

Each eligible subject will undergo 8-16 Study Visits; Screening, Day 1, Day 2, Day 3, Day 7, Day 14, Day 28, then every 4 weeks (total duration depends on assigned treatment group), followed by a Safety Follow-Up Visit, 4 weeks post-treatment. Study drug will consist of EBP-994 alone or in combination with either Norvir® and/or Pegasys®, depending on which group the subject has been randomized to on the Day 1 visit. Moreover, the investigator is free to initiate licensed medications at any time point and decrease the dose of EBP-994 if deemed warranted for GI side effects.

During the intervals between Study Visits, subjects will be free to carry on their usual activities of daily living. Subjects will be instructed to take their study medication at appropriate dosing intervals. Efforts should be made to schedule Study Visits according to the study protocol; however the window for consecutive Study Visits will be  $\pm 2$  days with the exception of Day 2 and Day 3 for which a visit window is not allowed.

Safety will be monitored by assessing vital signs, adverse events, concomitant medications, laboratory and ECG results. ECGs will be conducted and vital signs assessed at each Study Visit.

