## **6.9 *Study Visit 9-18 (Week 12-48) - Treatment Period***

Subjects are not to take their morning dose of study drug at home as pre-dose assessments are conducted at this visit.

7 Brief physical examination pre-dose (performed by a physician, nurse practitioner, physician's assistant or nurse). This includes weight and vital signs as well as HEENT, heart, lungs, abdomen and lower extremity.

8 Vital signs pre-dose

9 Concomitant medications will be recorded

10 Adverse events will be recorded

11 Laboratory studies (Pre-Dose) (non-fasting):

- p. Serum chemistry panel, including liver function tests and albumin
- q. Complete blood count (CBC with differential and platelet count)
- r. Quantitative PCR for HDV viral load
- s. Pre-dose blood samples (plasma and serum) for viral mutation analysis, resistance phenotyping, and analysis of drug mechanism and treatment response
- t. Urinalysis
- u. Blood sample for monitoring immunologic changes in peripheral blood mononuclear cells (PBMC).

12 Dosing Instructions:

Dosing with EBP-994 EBP-994 alone or in combination with Norvir® and/or Pegasys® should occur after the pre-dose vital signs have been taken, the physical examination performed, and pre-dose lab samples drawn. The subject should receive morning dose of study drug. If there is not sufficient drug remaining the subject may take the capsules from the container dispensed at this study visit. EBP-994 and/or Norvir® should be taken orally with 240 mL of water.

The container(s) of study drug(s) along with any unused drug dispensed at Study Visit 7 should be returned at this visit. Study personnel will perform drug accountability on the returned container(s) of study drug(s) to assess dosing compliance. A new container of drug will be dispensed at this visit to the subject. Subjects should be instructed to return all container(s) and any unused study medication at the next study visit. At each subsequent Study Visit, drug accountability will be performed for each subject to ensure that subject is compliant with dosing. Subjects should be instructed NOT to take their morning dose of study drug on the morning of the next Study Visit, Day 112, as pre-dose assessments will be conducted. Subjects should be sent home 3 hours post-dose.

If this is the last treatment visit, no new containers of drug(s) will be dispensed and all unused study medication will be collected.

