### **8.5 Pharmacokinetics**

Blood samples will be obtained for pharmacokinetics of EBP-994 at Study Visit 1 (Day 1) and Study Visit 6 (Day 28).

The following pharmacokinetic parameters will be calculated for EBP-994 on Day 1 using non-compartmental analysis, when applicable.

$AUC_{0-t}$ :	The area under the plasma concentration versus time curve, from time 0 to the last measurable concentration, as calculated by the linear trapezoidal method.
$AUC_{\text{inf}}$ :	The area under the plasma concentration versus time curve from time 0 to infinity. $AUC_{\text{inf}}$ is calculated as the sum of $AUC_{0-t}$ plus the ratio of the last measurable plasma concentration to the elimination rate constant.
$AUC/AUC_{\text{inf}}$ :	The ratio of $AUC_{0-t}$ to $AUC_{\text{inf}}$ .
$C_{\text{max}}$ :	Maximum measured plasma concentration over the time span specified.

---

$t_{max}$	Time of the maximum measured plasma concentration. If the maximum value occurs at more than one time point, $t_{max}$ is defined as the first time point with this value.
kel:	Apparent first-order terminal elimination rate constant calculated from a semi-log plot of the plasma concentration versus time curve. The parameter will be calculated by linear least-squares regression analysis using the maximum number of points in the terminal log-linear phase (e.g. three or more non-zero plasma concentrations).
$t_{1/2}$ :	Apparent first-order elimination half-life will be calculated as $0.693/kel$ .
CL/F:	The apparent total body clearance after extravascular administration, calculated as Dose/AUC inf
$V_{area/F}$ :	The apparent total volume of distribution after extravascular administration, calculated as Dose/(AUC inf x kel)

No value for kel, AUCinf or  $t_{1/2}$  will be reported for cases that do not exhibit a terminal log-linear phase in the concentration versus time profile.

Other PK parameters may be calculated if deemed appropriate.

The following pharmacokinetic parameters will be calculated for EBP-994 on Day 28 using non-compartmental analysis, when applicable.

$AUC_{0-t}$	The area under the plasma concentration versus time curve over the dosing interval at steady-state, as calculated by the linear trapezoidal method.
$C_{max,ss}$	Maximum measure plasma concentration over the time span specified.
$C_{min,ss}$	Measured plasma concentration at the end of the dosing interval.

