**APPENDIX A: SCHEDULE OF ASSESSMENTS**

EVENT	Screening	Day 1	Day 2	Day 3	Day 7	Day 14	Day 28	Treat wk 8	Treat wk 12-48	Follow wk 4
visit number	1	2	3	4	5	6	7	8	9-18	19
Informed consent	X									
Comprehensive physical exam	X									
Inclusion/exclusion criteria	X									
Medical history	X									
Concomitant medications	X	X	X	X	X	X	X	X	X	X
Adverse events			X	X	X	X	X	X	X	X
Weight	X	X								
Height	X	X								
BMI calculation	X	X								
Brief physical exam		X		X	X	X	X	X	X	X
Vital signs	X	X	X	X	X	X	X	X	X	X
12 lead ECG pre/post-dose 	X	X	X				X			X
Liver biopsy (if needed) 	X									
Complete blood count	X	X		X	X	X	X	X	X	X
Chemistry panel	X	X		X	X	X	X	X	X	X
Thyroid function	X									
Pregnancy test (serum)	X									
Pregnancy test (urine)		X								X
HBV DNA, HDV RNA	X	HDV RNA	HDV RNA	HDV RNA						
Viral mutation analysis 		X	X		X	X	X	X	X	X
HIV serology	X									
Urinalysis (pre-dose)	X			X	X		X	X	X	X
Urine drug screen 	X									
PBMC Collection	X	X	X	X	X	X	X	X	X	X
HCV viral load (quant PCR)	X									
PK sampling (pre-/post-dose) 	X	X	X	X	X	X	X	X	X	
INR	X									
Study drug administration		X			X					
Dispense study drug		X			X		X	X	X	
Study drug accountability			X		X		X	X	X	

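### Objective 4 asks for PK of treatment up to 48 weeks, but no PK result after Day 28 is planned, and Appendix A's PK schedule conflicts with the text

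*Combined protocol and SAP*

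**What the plan says.** The fourth primary objective, in the Protocol Summary and again in Section 2, is to "Evaluate the safety, tolerability, PK, and HDV viral load of a treatment up to 48 weeks" with EBP-994 alone or combined with Norvir and/or Pegasys.

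On sampling, Section 3 states: "Pharmacokinetic sampling will be done at Day 1 and Day 28 of dosing". It adds: "Participation in PK sampling is optional for each subject". Sections 6.2 (Day 1) and 6.7 (Day 28) list a 13-point profile from pre-dose to 12 hours. Sections 6.8 (week 8) and 6.9 (weeks 12 to 48) list no PK profile.

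On analysis, Section 8.5 states: "Blood samples will be obtained for pharmacokinetics of EBP-994 at Study Visit 1 (Day 1) and Study Visit 6 (Day 28". Appendix A numbers those days as visits 2 and 7. The last parameter set is introduced by "The following pharmacokinetic parameters will be calculated for EBP-994 on Day 28 using non-compartmental analysis, when applicable", and Section 8.5.1 compares Day 28 with Day 1 only.

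Appendix A differs. Its row "PK sampling (pre-/post-dose") is marked, as extracted, in every column from Screening to weeks 12-48; only the follow-up column is blank. Footnote 5 gives 12 time points over 0 to 12 hours and omits the 8-hour point.

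Separately, Section 6.9 collects "Pre-dose blood samples (plasma and serum) for viral mutation analysis, resistance phenotyping, and analysis of drug mechanism and treatment response" at each visit from week 12 to week 48. Section 6.2 names "determination of drug and potential metabolite levels in plasma" among the uses of this type of sample, and Section 6.3 repeats it. Section 8 plans no analysis of those levels.

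**The concern.** A primary objective names PK over a period for which the analysis section produces nothing, and sites are given two PK schedules that cannot both be followed.

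The gap matters because exposure can change after Day 28. Section 3 lets the investigator start licensed medications at any time point and reduce EBP-994 for GI side effects. Section 1.2 attributes the oxidative metabolism of EBP-994 to CYP3A, so an added drug that acts on that enzyme could also move exposure. Section 1.1 reports that viral-load change tracked mean drug level in the earlier HDV study. A viral-load rise at, say, week 24 or week 40 is harder to interpret if the drug level at that time is unknown.

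The scheduling conflict has its own cost: blood volume and site workload for subjects in the PK portion, and protocol deviations whichever schedule a site follows.

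**Working it through.** No power or sample-size figure underlies this point. The check sets the sections side by side and counts.

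**1. Time with no planned PK result (Sections 3, 6 and 8.5).** The last profile is on Day 28, that is, at week 4. Share of treatment after it = (duration − 4) / duration.
- 4 weeks: 0/4 = 0%
- 12 weeks: 8/12 = 67%
- 24 weeks: 20/24 = 83%
- 48 weeks: 44/48 = 92% (308 of 336 days)

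The documents do not say how many subjects receive each duration, so no study-wide figure can be given.

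**2. Samples per PK subject under Section 6.** Time points are 0, 15, 30, 60 and 90 min, and 2, 2.5, 3, 4, 6, 8, 10 and 12 h, which makes 13. Two profiles: 2 × 13 = 26.

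**3. Samples per PK subject under Appendix A, read literally, for 48 weeks.** Footnote 5 has the same list without 8 h, so 12 points. Weeks 12 to 48 at 4-week steps are 10 visits (visits 9 to 18), so visits 1 to 18 are marked.
- Without Screening: 17 × 12 = 204
- With Screening: 18 × 12 = 216
- After Day 28 (week 8 plus 10 visits): 11 × 12 = 132
- Ratio to the text, without Screening: 204/26 = 7.8

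**4. Can the Appendix A profile be done at those visits?** Screening precedes the first dose, so no post-dose sample exists. Sections 6.2 and 6.7 exempt PK participants from leaving 3 hours after dosing. Sections 6.3 to 6.6, 6.8 and 6.9 send all subjects home at 3 hours with no exemption. A 12-hour profile therefore fits the text only on Day 1 and Day 28.

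**5. What plasma already exists?** Sections 6.3, 6.5, 6.6, 6.7, 6.8 and 6.9 draw pre-dose plasma for drug-mechanism analysis on Days 2, 7, 14 and 28, at week 8 and at weeks 12 to 48. Subjects are told to withhold the morning dose before these visits, so each sample is taken before that day's first dose. Section 6.4 (Day 3) draws no such plasma, and Appendix A's viral-mutation row is also blank that day.

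**The case against.** The best reply is that objective 4 asks for PK of a treatment lasting up to 48 weeks, not PK at week 48. The treatment period can be as short as 4 weeks, and Section 6.7 allows Day 28 to be the last treatment visit. On that reading two profiles could be enough, and the objective only needs clearer wording. This stands as an alternative remedy. It does not justify leaving the text as it is, because the objective expressly covers longer treatment and the plan never says that Day 28 is meant to stand for it.

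A reader might infer that the objective cannot be answered at all. The documents do not support that. Plasma is drawn through week 48, drug levels are among its listed uses, and Section 8.5 permits other PK parameters and compartmental analysis. What is missing is a specified analysis, not the material. If Appendix A governs, even the sampling continues to week 48.

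A reader might also infer that resistance could not be told apart from under-exposure. That goes too far: mutation analysis, resistance phenotyping, drug accountability and the dosing diary give partial information. Nor do the documents say that exposure keeps drifting after Day 28. Section 1.2 reports metabolism-based CYP3A4 inhibition in vitro, but puts half-maximal CYP inhibition at several times the clinical peak concentration.

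Finally, Appendix A uses its labels loosely: the ECG row is also labelled pre/post-dose and is marked at Screening and follow-up. Not every PK mark need mean a full profile, so 204 is what a literal reading gives, not an expected burden. The table was extracted by a program and at least one other row is visibly incomplete, so the marks should be checked against the original.

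**Conclusion.** The point holds and should be fixed. Whichever schedule governs, Section 8.5 specifies no PK result after Day 28 for subjects treated longer than 4 weeks, although a primary objective covers treatment up to 48 weeks. The gap is 44 of 48 weeks for a 48-week subject, less for shorter durations, and none at 4 weeks. This part does not depend on how Appendix A was extracted.

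The second part is the conflict over visits and time points: 26 samples against about 204, a 12-point against a 13-point profile, a PK mark before any dose, and visit numbers 1 and 6 against 2 and 7. Its exact size assumes that the extracted marks are correct and that footnote 5 applies to each of them.

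The consequence is weaker interpretation of later viral-load changes, because Day 28 exposure cannot be taken to represent later exposure. That the plasma from Day 7 onward may be assayed for drug levels rests on reading the list of uses in Sections 6.2 and 6.3 as applying to the same sample type in Sections 6.5 to 6.9, where the list is not repeated.

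**What to change.** 1. After checking the original table, reconcile Appendix A with the text. Keep full profiles at Day 1 and Day 28 only. Delete the PK marks at Screening and Day 3. Align footnote 5 with the 13 time points of Sections 6.2 and 6.7. Change the visit numbers in Section 8.5 and the Protocol Summary from 1 and 6 to 2 and 7.
2. At Day 2, Day 7, Day 14, week 8 and weeks 12 to 48, mark a single pre-dose EBP-994 concentration from the plasma already drawn. State whether this covers all subjects or only those who consented to the optional PK portion.
3. Add to Section 8.5 a descriptive summary of pre-dose concentration by visit, randomised group and current dose, through the end of treatment, with a plot against HDV RNA at the same visit. Record the dosing interval with the dose, because Section 5.2 allows 8, 12 or 24 hours.

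This adds no visit and no venepuncture. The cost is the assays, a corrected table and a short addition to Section 8.5. If the sponsor does not want the assays, it should restrict the PK part of objective 4 to Day 1 and Day 28 and still make the corrections in step 1, with the remaining PK marks outside those two days also removed.
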